## 1、 Background

A choledochal cyst (CDC) is a congenital anomaly of the biliary system, which is more common in the Asian population . If a CDC is not diagnosed and treated promptly, it often leads to a series of serious complications, including cholangitis, cyst rupture, cholestatic cirrhosis, and even cholangiocarcinoma. Infants with a postnatal diagnosis of CDC often present with symptoms, and to avoid the occurrence of serious complications, operative correction should be performed as soon as possible when their clinical conditions allow. However, in the current era with the improvement of prenatal screening technology, an increasing number of choledochal cysts are diagnosed prenatally in the fetus. In developed countries, as many as 15% of choledochal cysts are found before birth . Some of these children receive intervention when they are asymptomatic at an early stage, while some have progressed to CDC-related symptoms before operative correction. The timing of operation for children with a prenatal diagnosis of CDC remains controversial. Redka et al. believed that infants with an antenatal diagnosis of CDC needed to be followed closely with ultrasonography and biochemical liver function tests and undergo elective reconstructive surgery at 3 months of age . In contrast, Diao et al. performed a prospective cohort study on asymptomatic children with a prenatal diagnosis of CDC and divided the children into an early ( $\leq 1$  month) operative group and a late ( $> 1$  month) operative group. They found that the extent of liver fibrosis was greater in the late operative group, and the postoperative recovery was statistically significantly delayed in patients with delayed surgery . Therefore, the authors recommended that operative correction should be performed in the neonatal period. In addition, Japanese clinical guidelines for pancreaticobiliary malformations suggest that symptomatic neonates and infants should be operated on as soon as possible. Elective operations should be considered for asymptomatic cases at approximately 3–6 months of age along with postnatal monitoring of organ functions, primarily of the liver, to determine if laboratory symptoms develop to warrant earlier intervention . Our previous study  showed that it is more advantageous to receive surgical treatment in the asymptomatic period for patients with prenatally diagnosed CDC. In addition, the age at operation (months) appears to be unrelated to intraoperative and postoperative complications, which is distinct from previous studies. More interestingly, we found that a specific cyst size (length  $> 5.2$  cm and width  $> 4.1$  cm)

suggested that clinical symptoms might appear and that the surgery should be performed as soon as clinically safe to proceed.

## **2、 Objective**

We tried to select the operation time according to the cyst size and evaluate the treatment effect.

## **3、 Study design**

The follow-up process from antenatal to perinatal was established, and the maximum diameter of postnatal cyst was used as the standard for the selection of surgical opportunity. The curative effect was evaluated by comparing with previous treatment schemes.

[figure not shown]
### **(1) Inclusion Criteria:**

- Infants with a prenatal and postnatal diagnosis with CDC
- Prenatal and postnatal hepatobiliary ultrasound data were complete
- Age of visit < 3 months

### **Exclusion criteria:**

- Unable to tolerate surgery after birth

### **(2) Flow Chart for prenatal diagnosis of choledochal cyst**

### Prenatal ultrasonography :

- (1) visibility of the right hepatic artery (RHA)
- (2) The maximum lumen length and maximum width of the GB and cyst from inner wall to inner ,as well as the wall thickness of the GB

#### 4、 Follow-up scheme

Follow-up scheme during the post-operative period included 1 week post-operative day, 1 month, 3-month, 6-month, then every year visits thereafter.

Follow-up Patients' follow-up after surgery mainly consisted of ultrasonography and biochemical tests (alanine aminotransferase (ALT), aspartate aminotransferase (AST),  $\gamma$ -glutamyl transpeptidase (GGT), and direct bilirubin (DBIL))

#### 5、 Outcomes and Efficacy Evaluation

(1) For the case-control studies, each patient treated with the new protocol was matched with two control patients treated with old protocol. Cases and controls were matched by all of the following: (1) gestational age at birth ( $\pm 2$  weeks), (2) birth weight ( $\pm 0.5$  kg), (3) gender, (4) Age of visit < 3 months, (5) All patients received laparoscopic-assisted CDC excision and hepaticojejunostomy.

(2) Old protocol: symptomatic neonates and infants should be operated on as soon as possible. Elective operations should be considered for asymptomatic cases at approximately 3–6 months of age along with postnatal monitoring of organ functions, primarily of the liver, to determine if laboratory symptoms develop to warrant earlier intervention

(3) Comparison of baseline material of patients in the two groups

The median estimated gestational age (EGA) , cyst diameter at the initial time of detection of the cyst, gestational age, cesarean rates, mean birth weight, sex ratio, age at operation in months, weight in kg at operation, type of CDC.

(4) Outcomes and Efficacy Evaluation

· Comparison of preoperative complications

preoperative symptom rate, cyst rupture, preoperative laboratory results performed within 1 week before the operation (ALT,AST, GGT, DBIL, TBIL, DBIL/TBIL)

- **Comparison of intraoperative conditions between the 2 groups.**

operative time in minutes, Body weight-corrected blood loss in ml/kg

- **Comparison of preoperative complications**

bile leakage、 anastomotic stricture、 bowel obstruction、 pancreatic

fistula、 incision dehiscence

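### The 1:2 matching to old-protocol controls uses no cyst measure, although the protocol itself links cyst size to symptoms, so a size difference between the series would bias the symptom comparison

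*Protocol*

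**What the plan says.** Section 5, item (1) of the protocol pairs each new-protocol infant with two old-protocol controls and lists the factors: "Cases and controls were matched by all of the following: (1) gestational age at birth" (within 2 weeks), birth weight (within 0.5 kg), gender, a first visit before 3 months of age, and the same laparoscopic-assisted operation. The last two are conditions that every infant meets, so the factors that really pair infants are gestational age, birth weight and gender.

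Cyst size appears elsewhere in the protocol:

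- The Background says of the group's earlier study: "More interestingly, we found that a specific cyst size" (length above 5.2 cm and width above 4.1 cm) "suggested that clinical symptoms might appear". It does not say whether that size was measured before or after birth.
- Section 3 bases the timing of surgery under the new protocol on postnatal maximum diameter, and describes the comparison so: "The curative effect was evaluated by comparing with previous treatment schemes".
- Section 5, item (3) includes "cyst diameter at the initial time of detection of the cyst" and the type of CDC in the baseline comparison. Postnatal diameter is not on that list.
- Section 5, item (4) names "preoperative symptom rate" as an outcome.

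**The concern.** Cyst size is the one marker of symptoms that the protocol itself puts forward, and symptoms before surgery are an outcome. The comparison is with earlier practice and is not randomised, so neither the design nor the matching balances size between the groups.

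The route to bias is narrow. Cyst size does not decide which protocol an infant receives; it guides timing within the new protocol. Bias therefore needs a difference in size case mix between the two series, for example if detection or referral changed over time. If the controls had larger cysts, the new strategy would look better than it is; if they had smaller cysts, it would look worse. The point concerns the symptom comparison only.

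**Working it through.** The protocol gives no sample size, symptom risk or size distribution, so there is no stated figure to reproduce. All numerical inputs below are assumptions, except the 1:2 ratio from Section 5. A true treatment effect of zero is assumed throughout.

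**(a) Two size strata, matching ignored.** Let q be the share of large cysts, and pL and pS the symptom risks with large and small cysts. The expected symptom rate in a group is q·pL + (1 − q)·pS, so the false difference is (gap in q) × (pL − pS). With q = 0.30 in the new group and 0.50 in the controls:

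- pL = 0.40, pS = 0.20: new 0.30×0.40 + 0.70×0.20 = 26%; controls 0.50×0.40 + 0.50×0.20 = 30%; false difference 4 points.
- pL = 0.50, pS = 0.10: new 0.30×0.50 + 0.70×0.10 = 22%; controls 0.50×0.50 + 0.50×0.10 = 30%; false difference 8 points.

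The false-positive rate of a two-sided 5% pooled z-test, by exact binomial enumeration with 50 v 100 infants and q = 0.30 in the new group, is:

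| Control share of large cysts, relative to new group | Risks 40%/20% | Risks 50%/10% |
|---|---|---|
| 20 points lower | 9.2% | 25.2% |
| 10 points lower | 6.2% | 9.9% |
| equal | 5.1% | 5.1% |
| 5 points higher | 5.2% | 5.7% |
| 10 points higher | 5.7% | 8.0% |
| 20 points higher | 7.8% | 17.5% |
| 30 points higher | 11.4% | 32.8% |

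Bias grows in importance with sample size. At 20 points higher, the rates for 30, 50 and 100 new-protocol infants are 6.3%, 7.8% and 10.7% (risks 40%/20%) and 11.7%, 17.5% and 30.6% (risks 50%/10%).

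**(b) Matched 1:2 sets.** Simulation with logit risk = −1 + set effect (SD 0.5) + ln(OR) × size, where size is standard normal and the control mean is shifted upwards; 6,000 runs per setting, simulation standard error about 0.3 points near 5%. False-positive rates of conditional logistic regression without size:

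| OR per SD of size | Sets | No shift | 0.25 SD | 0.5 SD |
|---|---|---|---|---|
| 1.6 | 50 | 4.6% | 5.4% | 7.9% |
| 1.6 | 100 | 4.8% | 6.5% | 12.2% |
| 2.5 | 50 | 4.6% | 6.9% | 17.0% |
| 2.5 | 100 | 4.9% | 10.8% | 30.3% |

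With size as a continuous covariate, all 12 settings lie between about 4.0% and 5.2%.

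**(c) Would a baseline test reveal the imbalance?** For a two-sided 5% test of mean size, power ≈ Φ(δ·√(n₁n₂/(n₁+n₂)) − 1.96), with δ in SD units. With 50 v 100, √(5000/150) = 5.77:

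- δ = 0.25: Φ(1.44 − 1.96) ≈ 30%.
- δ = 0.5: Φ(2.89 − 1.96) ≈ 82%.

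With 30 v 60 infants the powers are about 20% and 61%; with 100 v 200, about 53% and 98%.

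**The case against.** Leaving a prognostic factor out of the matching is not an error in itself, because it can be handled in the analysis, and covariate adjustment is commonly left to a statistical analysis plan, which is not at hand. The protocol does compare diameter at first detection and type of CDC between groups, and a baseline table is meant to show whether adjustment is needed. By the figures above, a 0.5 SD shift would be detected about 82% of the time with 50 v 100 infants, while the 0.25 SD shift that is often missed costs little (5.4% or 6.9% with 50 sets). No imbalance is shown, and the protocol gives no odds ratio to support the stronger settings; the 32.8% needs large-cyst shares of 30% v 60% and a five-fold risk.

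Much of this stands. It limits the point to a conditional one and makes the upper end of the tables illustrative only. It does not remove the point. The matching and baseline lists are fixed in this protocol and, followed as written, leave the factor it names uncontrolled. The power figures refer to the size variable itself; diameter at first detection is only a proxy for the postnatal diameter that drives the new strategy. A baseline comparison also describes an imbalance without correcting it.

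**Conclusion.** The concern holds as a cheap improvement, with medium confidence. The matching list contains no cyst measure, and the baseline list omits postnatal diameter, although cyst size is the protocol's own marker of symptoms and the comparison is not randomised.

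The size of any bias cannot be found from the document. Under the assumptions shown it is negligible for small imbalances. It matters only when the imbalance and the link between size and symptoms are both substantial: with 50 matched sets and a 0.5 SD shift, the false-positive rate is about 8% at an odds ratio of 1.6 per SD and about 17% at 2.5. Whether a separate analysis plan already adjusts for size cannot be told.

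**What to change.** Add early postnatal maximum cyst diameter to the baseline table for both groups. Adjust the symptom comparison for it as a continuous covariate in an analysis that respects the matched sets, for example conditional logistic regression. Take the value from the first postnatal scan, at a comparable early age in both groups and before the timing decision, so that the covariate is not itself shaped by the strategy.

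The cost is one covariate and one table line, provided the data exist. The inclusion criteria ask for this: "Prenatal and postnatal hepatobiliary ultrasound data were complete". However, the old protocol as described speaks of "postnatal monitoring of organ functions, primarily of the liver", so it must be confirmed that control records hold an early postnatal cyst measurement. If some do not, report how many and repeat the adjustment with diameter at first detection, which is already on the baseline list.

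Matching on a size stratum is an alternative only if enough controls remain; a size caliper could leave some infants with fewer than two. With few symptomatic infants, few matched sets are informative, so adjustment should stay at this one covariate.

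### The matching omits cyst size and CDC type, and the only listed cyst size is the diameter at first detection, which depends on gestational age at that scan; the symptom comparison should be adjusted, preferably for first postnatal diameter.

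*Protocol*

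**What the plan says.** The comparison is non-randomised. Section 3 (Study design) states: "The curative effect was evaluated by comparing with previous treatment schemes". No calendar period is given for either group.

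Section 5, item (1), sets the design: "each patient treated with the new protocol was matched with two control patients treated with old protocol". It introduces the factors with "Cases and controls were matched by all of the following" and names five: gestational age at birth (within 2 weeks), birth weight (within 0.5 kg), sex, a visit before 3 months of age, and laparoscopic-assisted excision with hepaticojejunostomy. Cyst size, gestational age at detection and CDC type are not among them.

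Those variables appear in item (3), whose stated purpose is "Comparison of baseline material of patients in the two groups". The list begins "The median estimated gestational age (EGA) , cyst diameter at the initial time of detection of the cyst" and ends "weight in kg at operation, type of CDC". EGA is most naturally read as the value at first detection, because gestational age is listed separately, but the wording is ambiguous. The "cyst diameter at the initial time of detection of the cyst" is the only cyst size listed.

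Section 3 makes the maximum postnatal diameter the criterion for timing surgery, and the inclusion criteria require complete prenatal and postnatal ultrasound. A postnatal diameter is nevertheless in neither the matching list nor the baseline list.

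The end of section 1 (Background) reports that, in the group's earlier study, a cyst length above 5.2 cm with a width above 4.1 cm pointed to symptoms. Item (4) compares preoperative symptom rate, cyst rupture and preoperative laboratory results.

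**The concern.** By the protocol's own account, cyst size is related to the first outcome compared. In a comparison with a previous scheme, such a variable should be balanced or adjusted for, and it should be measured so that it means the same thing in both groups. The protocol's matching does not balance it, and the one size it lists is taken at whatever gestational age the cyst was first seen.

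Two things could follow. First, if infants in one group were first scanned earlier in pregnancy, the raw diameters could differ when the cysts are alike, or agree when they differ. Two separate summaries, one of EGA and one of diameter, do not show whether cysts were the same size at the same gestation. Second, if one group contains more small or low-risk cysts, its symptom rate would be lower without any effect of the timing rule, and that difference would be credited to the new protocol or held against it.

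The Background gives a reason to take this seriously: "in the current era with the improvement of prenatal screening technology, an increasing number of choledochal cysts are diagnosed prenatally in the fetus". Prenatal diagnosis is an entry condition, so wider detection can change who enters the cohort.

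**Working it through.** The protocol gives no sample size, rate or expected difference on this point, so there is no figure to reproduce. The check has two parts.

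**1. The lists side by side**

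| Variable | Matched, item (1) | In baseline list, item (3) | Link to outcome or treatment in the protocol |
|---|---|---|---|
| Diameter at first detection | no | yes | size linked to symptoms (Background) |
| Postnatal diameter | no | no | maximum value decides timing (section 3); postnatal ultrasound required for inclusion |
| EGA at detection | no | yes, on the natural reading | fixes the time of the prenatal measurement |
| CDC type | no | yes | none stated |
| Calendar period | no | no | implied by a previous scheme |

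None of the five matching factors stands in for cyst size or for when and how the cyst was detected.

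**2. How large a distortion could be (every input assumed)**

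*Symptom rate.* Let s be the share of low-risk cysts. With no treatment effect,

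rate = s × (low risk) + (1 − s) × (high risk).

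Take s = 0.30 in the old group and 0.40, 0.50 or 0.60 in the new group.

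- Risks 10% and 40%: old 0.30 × 0.10 + 0.70 × 0.40 = 0.31; new 0.28, 0.25, 0.22. The fall is 3, 6 or 9 points.
- Risks 15% and 35%: old 0.30 × 0.15 + 0.70 × 0.35 = 0.29; new 0.27, 0.25, 0.23. The fall is 2, 4 or 6 points.

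The range is 2 to 9 points, or 7% (0.02/0.29) to 29% (0.09/0.31) relative. Exchanging the two shares reverses the sign.

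*False significance.* A second set of assumptions: symptom risk 20% with a small cyst and 40–60% with a large one; large cysts 25% new v 35% old, up to 20% v 40%. At the mild end, new = 0.25 × 0.40 + 0.75 × 0.20 = 0.25 and old = 0.35 × 0.40 + 0.65 × 0.20 = 0.27, a difference of −2 points. At the strong end, new = 0.20 × 0.60 + 0.80 × 0.20 = 0.28 and old = 0.40 × 0.60 + 0.60 × 0.20 = 0.36, a difference of −8 points.

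For n new and 2n old infants treated as independent, two-sided 0.05, with d the absolute difference:

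P(reject) = Φ((d − 1.96 × se0)/se1) + Φ((−d − 1.96 × se0)/se1), where se0 uses the pooled rate and se1 the separate rates.

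Strong end, 80:160: pooled rate = (80 × 0.28 + 160 × 0.36)/240 = 0.333; se0 = √(0.2222 × (1/80 + 1/160)) = 0.0645; se1 = √(0.2016/80 + 0.2304/160) = 0.0629; P = Φ(−0.74) + Φ(−3.28) ≈ 0.23.

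| New : old | Mild end | Strong end |
|---|---|---|
| 20:40 | 5.1% | 8.9% |
| 40:80 | 5.4% | 13.5% |
| 80:160 | 6.1% | 23% |

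With equal case mix the difference is 0 and the rate stays at 5%. More infants make a given bias more likely to reach significance.

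*Prenatal diameter.* At an assumed growth of 0.5–1 mm per week, a scan 4–6 weeks earlier makes the same cyst look 0.5 × 4 = 2 mm to 1 × 6 = 6 mm smaller.

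**The case against.** The strongest reply is that no imbalance is shown. A reader might infer that better screening has moved detection to an earlier gestational age, so that first-detection diameters cannot be compared between eras. The Background does not say this. It reports more prenatal diagnoses, not earlier or milder ones; it describes a general trend, not these two groups; and without calendar periods the groups may be close in time with similar ultrasound practice. EGA is also listed beside the diameter, so a shift in detection timing would be visible. All of this stands, and the era effect is therefore only a possibility. What remains is that seeing a shift in EGA neither puts the diameters on a common footing nor takes the shift out of the outcome comparison.

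A reader might also infer that nothing will remove an imbalance. That goes too far: covariate adjustment is commonly left to the statistical analysis plan, which is not at hand, and item (4) neither specifies nor excludes a model. Only the matching set and the list of baseline variables are fixed here. A later plan that adjusted for the one listed diameter alone would still carry its dependence on scan timing.

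Finally, both a prenatal and a postnatal diagnosis are required, and every matched infant had the operation. If controls met the same entry criteria, cysts that resolved or never came to surgery are absent from both groups. This narrows the route by which milder cysts could enter one group, but does not close it.

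**Conclusion.** The point holds in a limited form. The matching omits cyst size and CDC type; the only listed cyst size is measured at a gestational age that can vary between infants and groups; and the protocol itself treats size as related to symptoms. If the groups differ in detection timing or in the range of cysts detected, the crude diameter comparison may mislead, and the matching does not protect the symptom comparison.

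Neither the size nor the direction of any bias can be derived from the protocol. The 2 to 9 points, the false-positive rates of up to 23% and the 2 to 6 mm rest wholly on assumed mixes, risks, group sizes and growth. They show that a modest imbalance could matter, not that one exists. The change is worth making because it is cheap and the design is non-randomised. The most useful variable is the first postnatal diameter: it does not depend on when in pregnancy the cyst was found, and the required ultrasound record should contain it.

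**What to change.** In section 5, item (3):

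- Add the cyst diameter at the first postnatal scan, with age at that scan. Use the first scan rather than the largest value up to surgery, because the time available to reach a maximum depends on when surgery is done.
- State that EGA means gestational age at the detection scan, and compare the prenatal diameter conditional on it, for example by regressing diameter on EGA and group.
- State the calendar period of each group.

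In item (4), or by reference to the analysis plan:

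- Estimate the group difference adjusted for first postnatal diameter (or, failing that, the EGA-adjusted prenatal diameter) and CDC type. Fix this in advance, whatever the baseline table shows.
- Keep the 1:2 matched sets in the analysis. If events are few, use a single propensity score or a Firth-penalised model.
- Do not adjust for age or weight at operation: both are in the baseline list, but the timing rule itself affects them.

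The cost is wording, plus extraction of one measurement from scans that inclusion already requires; that controls met the same requirement is an assumption the protocol should confirm. With small numbers only two or three covariates can be carried, so size and CDC type should come first.

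### Fifteen efficacy comparisons are listed under three headings with none designated primary, so a mixed result has no pre-set reading

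*Protocol*

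**What the plan says.** The objective (section 2) is: "We tried to select the operation time according to the cyst size and evaluate the treatment effect". The design (section 3) adds: "The curative effect was evaluated by comparing with previous treatment schemes". Neither says which outcome carries the treatment effect.

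Section 5(4) then lists what is to be compared between new-protocol patients and their matched old-protocol controls, in three headed groups:

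- Before surgery: "preoperative symptom rate, cyst rupture, preoperative laboratory results performed within 1 week before the operation". These are two clinical outcomes and six laboratory measures (ALT, AST, GGT, DBIL, TBIL and the ratio of DBIL to TBIL).
- During surgery: "operative time in minutes, Body weight-corrected blood loss in ml/kg".
- Surgical complications: "bile leakage、 anastomotic stricture、 bowel obstruction、 pancreatic" and, continuing on the next line, "fistula、 incision dehiscence".

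The heading of the third group repeats that of the first and calls its items preoperative, although they arise from the operation. This looks like a labelling slip and does not affect the count. No outcome is called primary, main or secondary anywhere in the protocol.

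**The concern.** Tests, significance levels and multiplicity methods may be left to a statistical analysis plan, and their absence here is not the complaint. Which outcome answers the study question is different: that belongs in the protocol, and this protocol sets out its efficacy section without deciding it.

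The consequence is sharper because the study compares timing strategies. Operating at a different time could lower the rate of symptoms before surgery and also change operative time, blood loss or complications. The outcomes can therefore point in different directions. With no deciding outcome, a mixed result can be written up as success by stressing the items that favour the new protocol. A reader could not tell such emphasis from a planned conclusion.

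**Working it through.** There is no sample size, power or significance level in the protocol, so there is no stated figure to reproduce. The check is a count followed by an illustration.

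**Count (section 5(4)).** 2 clinical preoperative + 6 laboratory + 2 intraoperative + 5 complications = 15.

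**Assumptions, not in the protocol.** Each comparison is tested at two-sided 5%, which is 2.5% in the direction favouring the new protocol. There is no true difference on any outcome. Correlations are set by assumption and shown as a range.

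**Independent outcomes.**
- Either direction: 1 − 0.95^15 = 0.537.
- Favouring the new protocol: 1 − 0.975^15 = 0.316.

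**Laboratory values correlated at 0.6, other nine independent.** Simulating six normal test statistics with common correlation 0.6 gives a chance of at least one nominal difference of 0.187 in either direction and 0.094 in the favourable direction. Combining these with the nine others:
- Either direction: 1 − (1 − 0.187) × 0.95^9 = 1 − 0.813 × 0.630 = 0.49.
- Favourable: 1 − (1 − 0.094) × 0.975^9 = 1 − 0.906 × 0.796 = 0.28.

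**All 15 correlated at 0.5.** By simulation, 0.36 in either direction and 0.18 favourable.

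**Rare events contribute nothing.** Cyst rupture and the five complications may be too uncommon to reach significance. Dropping all six leaves 15 − 6 = 9 outcomes: the six laboratory values (at 0.6) and three others.
- Either direction: 1 − 0.813 × 0.95^3 = 1 − 0.813 × 0.857 = 0.30.
- Favourable: 1 − 0.906 × 0.975^3 = 1 − 0.906 × 0.927 = 0.16.

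| Scenario | Favouring new protocol | Either direction |
|---|---|---|
| 15 independent | 31.6% | 53.7% |
| Laboratory values at 0.6, rest independent | 28% | 49% |
| All 15 at 0.5 | 18% | 36% |
| Six rare events drop out, laboratory values at 0.6 | 16% | 30% |
| One primary outcome | 2.5% | 5% |

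As an extreme, a common correlation of 0.8 across all 15 still gives about 10% favourable and 20% in either direction.

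For a claim that the new protocol is better, the favourable column is the relevant one. The first four rows are 0.316 / 0.025 = 12.6 to 0.16 / 0.025 = 6.4 times the single-primary rate.

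**The case against.** The strongest reply is that the protocol is silent rather than wrong. It gives no test, no level and no decision rule. A reader might infer that the 15 outcomes form one undifferentiated list of equal weight, and that a significant result on any of them would be taken as proof of benefit. The protocol says neither. The outcomes stand under three headings, and preoperative symptom rate comes first, which fits the Background's reason for choosing a cyst-size cut. This part of the objection stands, and the stronger reading should not be attributed to the protocol.

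The numbers also need restraint. The 53.7% figure counts chance differences in favour of the old protocol as well, so it does not measure the risk of wrongly calling the new protocol better. Treating rare complications as tests with a full 5% error rate overstates the risk, and the ratio of direct to total bilirubin is computed from two other listed values. These corrections roughly halve the independent-case favourable figure, from 31.6% to 16–18%; they do not bring it near 2.5%.

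A further objection is that symptom rate is an imperfect sole arbiter. A strategy that changes when surgery happens also changes how long a child has in which to develop symptoms beforehand. That is right. It rules out letting the whole judgement of benefit rest on that outcome, but not naming a primary outcome.

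Finally, the comparison is not randomised, and naming a primary does nothing about confounding. That is a separate matter and adds no weight here.

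What the objection does not remove is the gap itself: being first in a list is a hint, and a hint does not bind the conclusion.

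**Conclusion.** The point holds in a limited form. The protocol lists 15 efficacy comparisons, designates none as primary, and names no deciding outcome in its objective or design. A mixed result therefore has no pre-set reading, and selective emphasis cannot be ruled out.

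The chance of at least one nominal difference favouring the new protocol, when there is no true difference, runs from about 16% to 31.6% across the four main scenarios, against 2.5% for one primary. These rates are illustrative: they rest on an assumed two-sided 5% level per comparison, assumed correlations and, for the lowest figure, an assumption that rupture and complications are rare. The lack of a pre-set reading does not depend on them.

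The study is not invalidated, but the wording should be changed.

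**What to change.** In section 5(4):

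1. Designate one primary outcome. Preoperative symptom rate is the natural candidate, because the Background presents the cyst-size cut as a sign that symptoms might appear. If the sponsor prefers another listed outcome, the essential step is still to name one.
2. Label the other 14 outcomes secondary and report them as estimates with 95% confidence intervals. Any multiplicity procedure for them can be left to the analysis plan.
3. State that the efficacy claim is tested on the primary outcome, and that operative measures and complications are reported beside it as the counterweight in judging overall benefit.
4. Show age at operation with the symptom rate, since that rate partly reflects how long each child waits for surgery. Section 5(3) already lists age at operation, so nothing extra has to be collected.

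The cost is protocol wording only, with no new data. The downsides are that a chance difference on a secondary outcome can no longer carry the efficacy claim, and that the chosen primary has to be read together with waiting time.
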